## **1.6 Procoagulant effects of MSCs**

Although MSCs have been safely used in numerous clinical trials, preparations of these cells may express Tissue Factor and therefore pose an increased thrombogenic risk [64-67]. Thus the general safety of bone marrow derived MSCs [68] has been accompanied by reports of thrombotic and embolic complications in animal and human studies when the MSCs were derived from alternative sources such as adipose tissue or placental tissue [65, 69-73]. MSC from these sources may express higher levels of TF [74, 75] than BM derived MSCs, potentially accounting for the observed “instant blood-mediated inflammatory reactions” (IBMIR) [76, 77].

The TF expression of adipose and placenta derived MSC shows significant variation depending on donor and culture passage [66, 70, 78, 79]. Although these thrombotic complications are rarely seen after infusion of BM derived MSCs, low dose anticoagulation has been used preclinically and in human studies [72, 74, 75, 80, 81]. These additives block activation of coagulation and complement, decreasing the risk of IBMIR-triggering. Thus, supplementation with anticoagulants appears to be a simple method to reduce activation of coagulation pathways following MSC infusion, which might also enhance the therapeutic effect. Thus in an effort to mitigate any putative additional procoagulation activity following infusion of MSCs, patients with active COVID 19 disease must be eligible for prophylaxis with LMWH/UFH.

## **2 Study Design**

### **2.1 Study Overview**

This study is a single center open label, non-blinded randomized, controlled study designed to evaluate the use of single donor banked bone marrow derived MSCs versus standard of care as therapy for patients with ARDS due to COVID-19 disease. The study will first enroll and treat six patients with MSCs for safety run in. If no more than 2 treatment-related severe adverse events (tSAEs) are observed, the study will enroll and randomize additional 60 patients in a ratio of 1:1 to receive either MSCs or routine/supportive care.

### **2.2 Hypothesis and Specific Objectives**

#### **2.2.1 Primary Hypothesis**

The primary hypothesis is that banked, bone marrow derived mesenchymal stromal cells can be safely used to mediate the severe inflammatory response seen in moderate or severe ARDS resulting from COVID-19 disease compared to the control group receiving routine supportive care.

## **2.3 Study Objective:**

To evaluate the safety and clinical benefits of banked mesenchymal stromal cells (MSCs) versus control for treatment of patients with COVID-19 induced ARDS.

### **2.3.1 Primary endpoints:**

1. Treatment-related serious adverse events (tSAEs)
2. Improvement by at least two categories on a six category ordinal scale at day 14 post randomization. The six-category ordinal scale is as follows:  
6 = death; 5 = hospitalization, requiring extracorporeal membrane oxygenation (ECMO) and/or invasive mechanical ventilation (IMV); 4 = hospitalization, requiring non-invasive mechanical ventilation (NIV) and/or High-flow nasal cannula (HFNC) therapy; 3 = hospitalization, requiring supplemental oxygen (but not NIV/HFNC); 2 = hospitalization, not requiring supplemental oxygen; 1 = hospital discharge.

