### **2.3.2 Secondary endpoints:**

1. Clinical status at day 28 as determined by 6-point ordinal scale
2. Severity of ARDS at day 14
3. Oxygenation free days at day 28
4. Progression to mechanical ventilation or ECMO
5. Duration of mechanical ventilation and/or ECMO (ventilation/ECMO free days at day 28)
6. Duration of ICU stay (ICU free days at day 28)
7. Duration of hospital stay (time to discharge)
8. Overall survival
9. All-cause mortality at day 28

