### 7.2 Post-randomization/treatment Evaluation

- 7.2.1. History and physical (including vitals and oxygenation requirements) daily during hospitalization
- 7.2.2 ARDS assessment daily day 0 through 7, then weekly until day 28 if remains intubated in the ICU or until extubated, whichever occurs first, and ABG data available
- 7.2.2. The following routine laboratory investigations will be obtained through day 7, then weekly until day 28 or hospital discharge, whichever comes first
  - CBC
  - CMP
- 7.2.3. PT/aPTT, d-dimer, fibrinogen, CRP and LDH will be collected from the medical record, if available, at timepoints noted in the study calendar.
- 7.2.4. CXR and/or CT chest imaging will be done at baseline, then as then as clinically indicated per treating physician discretion. Data will be collected from the medical record, if available, at timepoints noted in the study calendar.
- 7.2.5. SOFA/CURB-65 score day 0, and day 28, if patient remains in the ICU and ABG available per SOC (for SOFA calculation).
- 7.2.6. Research cytokine profile and labs day 0 pre-infusion, 3-4 hours post-infusion, day 1, 3, 5, 7, 14 and day 28 if remains hospitalized. Optional if patient has

been discharged.

- 7.2.7.** Medical record review for data collection on supportive interventions, including but not limited to:
- Respiratory support (high flow nasal canula, AirVO, proning, high frequency oscillatory ventilation (HFOV), etc.)
  - Pharmacologic interventions (corticosteroids, vasopressors, paralytics, pulmonary vasodilators, etc.)
- 7.2.8.** Medical record review for data collection on concurrent medications (such as antibiotics, antivirals, antihypertensives, anticoagulants), concurrent infections, and other end-organ damage daily through day 28 or hospital discharge, whichever occurs first
- 7.2.10.** Clinical status assessed by the six category ordinal scale daily until hospital discharge or death, whichever occurs first.

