### **7.3 Follow up**

- 7.3.1.** If discharged from the hospital prior to day 28, patients will followed up with (in clinic or by telephone) through day 28 as outlined in study calendar Section 6.1. Additional visits or telephonic contacts will be obtained as clinically indicated for patients with toxicities deemed to be related to the MSC infusion, which will be followed until resolved.

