### **8.2 Sample size**

This early phase study will accrue a total of 66 patients with 6 patients for safety run in and additional 30 patients in each treatment arm by randomization. MSCs will be manufactured in our GMP facility and available to treat at least 36 patients. The study primary efficacy endpoint is improvement in clinical status at least two categories on a six-category ordinal scale at day 14 post randomization. The six-category ordinal scale ranges from 6 to 1 with a higher score indicates worse clinical outcome, i.e. 6 = death; 5 = hospitalization, requiring ECMO and/or IMV; 4 = hospitalization, requiring NIV and/or HFNC therapy; 3 = hospitalization, requiring supplemental oxygen (but not NIV/HFNC); 2 = hospitalization, not requiring supplemental oxygen; 1 = hospital discharge. The scale will be used to evaluate patients' status daily from baseline to day hospital discharge. Patients' clinical status at day 14 post randomization will be dichotomized as 'improved' (decreased by at least two categories) or 'not improved'. Patients who died before day 14 will be deemed as 'not improved'. Public data about the novel COVID-19 are limited and the data varies between all studies. Based on reported data, the time to improvement in patients with supportive care were about 22-23 days [20, 82] we expect 10% patients in the control group and 35%

patients in the MSC group will achieve 'improved' status at day 14, a total sample size of 66 (36 in the MSC arm and 30 in the control arm) will provide 84% power to detect a difference in clinical improvement of 25% between control (10%) and MSC (35%) at a 7.5% one-sided significance level using a Chi-square test.

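### Category 1 is an unqualified hospital discharge, so some live hospice discharges and discharges on ventilatory support count as improved, and transfers have no scoring rule

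*Combined protocol and SAP*

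**What the plan says.** Sections 2.3.1 and 8.2 both set out the scale in full. Its last two categories are "2 = hospitalization, not requiring supplemental oxygen; 1 = hospital discharge". Section 7.1.13 only abbreviates category 1. Nowhere is discharge qualified by destination, continuing respiratory support or goals of care, and neither hospice nor transfer between facilities is mentioned.

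Category 5 is given in 8.2 as "5 = hospitalization, requiring ECMO and/or IMV". Categories 2 to 5 all use the word hospitalization without saying at which institution.

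For the primary efficacy endpoint, day-14 status "will be dichotomized as 'improved' (decreased by at least two categories) or 'not improved". There is one override: "Patients who died before day 14 will be deemed as 'not improved".

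On timing, 7.2.10 reads "Clinical status assessed by the six category ordinal scale daily until hospital discharge or death, whichever occurs first", and 8.2 likewise runs the daily scoring up to discharge. The study calendar in 6.1 nevertheless lists the scale at days 14, 21 and 28. Its footnote there calls for daily scoring while the patient is in hospital; it is not the footnote that confines other items to patients still in hospital. Section 7.3.1 says that, after an early discharge, "patients will followed up with (in clinic or by telephone) through day 28". Neither place says how a patient who has left is to be scored.

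**The concern.** The scale's best category is reached by leaving hospital, whatever the patient's condition on leaving. Entry requires moderate or severe ARDS (3.1), so patients will in practice start at category 3, 4 or 5 (an inference; the protocol does not say so). From any of these, a score of 1 is a fall of at least two and therefore a success.

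In this population some patients may leave hospital without having recovered. If they are scored 1, treatment failures enter the primary endpoint as successes. Equal misscoring in both arms dilutes the difference and costs power. Unequal misscoring would bias the comparison in either direction. The trial is open label (8.1) and no blinded assessor of the scale is described, so where the wording allows two scores the choice falls to staff who know the arm. The same undefined event also feeds day-28 clinical status and time to discharge among the secondary endpoints (2.3.2).

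**Working it through.** **Step 1. Apply the rule as written to each kind of departure.**

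| Departure by day 14 | Score under the text | Result |
|---|---|---|
| To hospice, dies before day 14 | overridden by the death rule in 8.2 | not improved |
| To hospice, alive at day 14 | 1; no other category fits | improved |
| On ventilatory support to a non-hospital facility | 1; no other category fits | improved |
| Transferred on IMV or ECMO to another hospital or long-term acute care facility | 1 (discharged from the study hospital) or 5 (still hospitalized on IMV/ECMO) | improved or not improved |

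The second and third rows are wrong as written. The fourth is undetermined.

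**Step 2. Reproduce the plan's power.** Inputs from 8.2: control 10% (n = 30), MSC 35% (n = 36), one-sided 7.5%, Chi-square; z = 1.4395.
- Pooled rate = (3 + 12.6)/66 = 0.2364.
- Null SE = √[0.2364 × 0.7636 × (1/30 + 1/36)] = 0.1050.
- Alternative SE = √(0.10 × 0.90/30 + 0.35 × 0.65/36) = 0.0965.
- Power = Φ[(0.25 − 1.4395 × 0.1050)/0.0965] = Φ(1.02) = 84.7%, against 84% stated.

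The plan's figure reproduces, and this point does not affect that arithmetic.

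**Step 3. Move to the population analysed.** Section 8.5 bases efficacy on eligible randomized patients, which is 30 v 30. Summing binomial probabilities over all outcomes for which the uncorrected one-sided Chi-square rejects gives 83.6% power at 10% v 35%, and 6.9% rejection at 10% v 10%.

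**Step 4. Illustrate misscoring.** Assumption: a share q of true non-improvers is scored improved, equally in both arms. The documents give no value for q. Observed rates become 0.10 + 0.90q (control) and 0.35 + 0.65q (MSC).

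| q | Control | MSC | Difference | Power, 30 v 30 |
|---|---|---|---|---|
| 0 | 10.0% | 35.0% | 25.0 | 83.6% |
| 2% | 11.8% | 36.3% | 24.5 | 80% |
| 5% | 14.5% | 38.3% | 23.8 | 75% |
| 10% | 19.0% | 41.5% | 22.5 | 68% |

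**Step 5. Size of one patient.** 1/30 = 3.3 points, against an assumed control rate of 10%. At 3/30 in the control arm, 7/30 on MSC gives z = 1.39 (not significant against 1.44) and 8/30 gives z = 1.67 (significant). A single score can therefore decide the test near the boundary.

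**The case against.** Three stronger readings are tempting, and the documents do not support them.

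- *Every transfer on support scores 1.* Because categories 2 to 5 do not tie hospitalization to the study hospital, a patient moved elsewhere for ECMO or on IMV fits category 5. A score of 1 is one reading, not the rule. What stands is that the plan does not choose between the two, and 7.2.10 stops scoring at discharge.
- *Every hospice discharge becomes a success.* A patient who dies before day 14 is already not improved under 8.2. Only hospice patients alive at day 14 are affected.
- *The type I error is inflated.* If misscoring occurred in the MSC arm only, with no true effect, the enumeration above would give rejection rates of 10.6%, 17.7% and 32.6% for q = 2%, 5% and 10%, against 6.9%. But nothing in the documents indicates that departures would be confined to one arm, so these figures cannot measure the problem.

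It can also be said that the calendar schedules a day-14 assessment and 7.3.1 provides the contact, so status after discharge could be captured. That is fair, and it makes the fix cheap. It does not supply a rule: it sits in tension with 7.2.10, and a person who has been discharged to a non-hospital setting still has only category 1 available. Mortality and ventilator-free days would partly expose such cases, but would not correct the primary endpoint.

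**Conclusion.** The point holds in a limited form. For two kinds of patient, those discharged to hospice and alive at day 14 and those discharged on ventilatory support to a non-hospital facility, the written rule gives a wrong primary-endpoint result. For patients transferred on IMV or ECMO it gives no single result and leaves the choice to unblinded staff.

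The size cannot be found from the documents. My judgement is that such departures are probably few. The fall in power to between 80% and 68% rests wholly on the assumed 2% to 10% misscoring in both arms, and on the plan's own 10% and 35%. It illustrates sensitivity and is not a forecast. The reason to act is that the gap sits in the primary efficacy endpoint of a small open-label trial and can be closed by wording.

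**What to change.** In 2.3.1 and 8.2:
- Define category 1 as discharged alive, not to hospice, and not on IMV, NIV or HFNC.
- State that hospitalization in categories 2 to 5 includes any acute or long-term acute care facility. A transferred patient is then scored by respiratory support at day 14, carrying forward the category at transfer if later status is unknown.
- State that a patient discharged on IMV, NIV or HFNC to any other setting is scored by that support. A condition on setting alone would not be enough, because a ventilated patient in a nursing facility would still score 1.
- State that a live discharge to hospice is not improved and is not an event for time to discharge, and say whether it is censored or treated as a competing event there.

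Apply the same rules to clinical status at day 28. Reconcile 7.2.10 with the day-14, 21 and 28 ordinal-scale entries in 6.1. Record discharge destination and respiratory support at discharge on the CRF.

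The cost is protocol and SAP wording and a small CRF addition; later status can be collected at contacts already scheduled in 6.1 and 7.3.1. Treatment, sample size and test are unchanged. The observed improvement rate may be slightly lower.

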### **2.3.2 Secondary endpoints:**

1. Clinical status at day 28 as determined by 6-point ordinal scale
2. Severity of ARDS at day 14
3. Oxygenation free days at day 28
4. Progression to mechanical ventilation or ECMO
5. Duration of mechanical ventilation and/or ECMO (ventilation/ECMO free days at day 28)
6. Duration of ICU stay (ICU free days at day 28)
7. Duration of hospital stay (time to discharge)
8. Overall survival
9. All-cause mortality at day 28

### **2.3.3 Exploratory endpoints**

1. Changes in inflammatory markers (CRP, IL-6, IL-10, TNF- $\alpha$ )
2. Negative SARS-CoV-2 RT-PCR by day 28 (if available)
3. Changes in blood safety laboratories (CBC with differential, electrolytes, renal indices, liver function studies, LDH, coagulation studies if available)
4. Corticosteroid use and duration
5. Changes in chest imaging
6. Evolution of other end-organ damage (hepatic, renal, cardiovascular)
7. Changes in disease severity score (SOFA, CURB-65)
8. Duration of vasopressor use

## **3 Eligibility Criteria**

### **3.1 Inclusion Criteria**

- 1) 18 years or older

- 2) Confirmed SARS-CoV2 infection real-time reverse transcription polymerase chain reaction (RT-PCR) assay
- 3) Moderate OR severe ARDS, based on the degree of impairment of oxygenation as defined by the ratio of arterial oxygen tension to fraction of inspired oxygen ( $\text{PaO}_2/\text{FiO}_2$ ):
  - a. Moderate ARDS:  $\text{PaO}_2/\text{FiO}_2$  100-200 mmHg
  - OR**
  - b. Severe ARDS:  $\text{PaO}_2/\text{FiO}_2 \leq 100$  mmHg
- 4) If on invasive or noninvasive (BiPAP) mechanical ventilator,  $\text{PEEP} \geq 5$  cm  $\text{H}_2\text{O}$
- 5) Bilateral opacities present on chest radiograph or computed tomographic (CT) scan, that are not fully explained by pleural effusions, lung collapse, or lung nodules.

## **4 Mesenchymal Stromal Cells (MSCs) Manufacturing**

All manufacturing procedures will be performed in our GMP facility as dictated by Standard Operating Protocols (SOP). Brief summaries are given here.

### **4.1 Source Material. The cell product will consist of allogeneic mesenchymal stromal cells**

MSCs) generated from the bone marrow of an eligible normal donor. Up to 100 ml of marrow is obtained by aspiration under local anesthesia following informed consent. The donor will meet the eligibility requirements as described in 21 CFR Parts 1271 Subpart C. Testing ([Table 1](#)) will be performed using FDA-approved, cleared and/or licensed kits by Gulf Coast Regional Blood Center within 7 days of collection of the

marrow for manufacturing. Manufacturing commences within four hours of marrow collection by following [SOP L03.05.XX](#). (Expansion of Human Mesenchymal Stromal Cells from Bone Marrow Using the Quantum Cell Expansion System).

**Table 1** Infectious Disease Testing on Marrow Donor

Test	Specification
Chagas Disease	Negative
Hepatitis B Surface Antigen	Negative
Hepatitis B Core	Negative
Hepatitis C Virus	Negative
HIV 1 and 2	Negative
HTLV I and II	Negative
TAQ Screen MPX (HBV,HCV, HIV-1 Group M RNA, HIV-1 Group O)	Negative
NAT West Nile Virus	Negative
Serological Test for Syphilis	Negative

**4.2 Ex vivo cell expansion. In order to meet the cell dose requirements for the protocol, a**

primary cell bank will be established. This will consist of MSCs cultured to passage 2 from the marrow using the Terumo Quantum Bioreactor (a Master File on this device has been filed by Terumo BCT). This system avoids the multiple open procedures associated with culturing the cells in cell culture flasks, thereby considerably decreasing the risk of contamination. The cell culture bioreactor and all tubing are sterile and completely disposable, thereby avoiding the possibility of cross-contamination. The Quantum is capable of generating more than 1.5 billion MSC at Passage 2.

**4.3 Freezing. For this proposal, we will use cells that were previously grown to**

passage 2 and frozen in aliquots suitable for future expansion. The pooled passage 2 cells were tested for sterility, endotoxin, and mycoplasma following previously validated SOPs. The cells are frozen in Plasma Lyte containing a final concentration of 10% v/v DMSO using a controlled-rate freezer and stored in the vapor phase of liquid nitrogen (SOP [C03.34.XX](#)). The cell products for administration will be thawed Passage 3 cells generated from aliquots of the Passage 2 frozen cell bank. Passage 2 cells will be thawed and seeded into the Quantum bioreactor, cultured and harvested, washed, counted, and cryopreserved using a controlled rate freezer in Plasma Lyte A containing 10% DMSO following standard operating procedures (SOPs [L03.05.XX](#) and [C03.34.XX](#)).

- 4.4 Testing. Products that meet study specific release criteria, as detailed on the certificate of analysis (CofA), will be infused as per Section 4.0.**

## **5 Patient Enrollment and Evaluation**

### **5.1 Informed Consent**

Informed consent should be obtained prior to enrollment on the study. All patients and/or their legal guardian must sign a document of informed consent consistent with local institutional and federal guidelines stating that they are aware of the investigational nature of this protocol and of the possible side effects of treatment. Further, patients must be informed that no efficacy of this therapy is guaranteed, and that unforeseen toxicities may occur. Patients have the right to withdraw from this protocol at any time. No patient will be accepted for treatment without such a document signed by him or his legal guardian. Full confidentiality of patients and patient records will be provided according to institutional guidelines.

### **5.2 Registration and Randomization**

All consented patients will be registered in the online collaborative research environment (Forte's OnCore® eResearch CTMS), a Clinical Research Management System available at BCM Dan L. Duncan Comprehensive Cancer Center. Prior to enrollment in the study, the eligibility data must be reviewed and verified by the study coordinator and treating physician. After the eligibility status is verified, the subject will be assigned to a unique study sequence number. After safety run in, additional patients will be randomized in a 1:1 ratio to either the MSC or control arm. Randomization will use the permuted block method and be stratified by severity of ARDS (moderate and severe). Randomization information will be stored on a secure, access-restricted server at Baylor College of Medicine.

### **5.3 Treatment Plan**

#### **5.3.1 Dosing**

Patients who are randomized to the MSC arm will be administered an intravenous infusion of MSCs at a dose of  $1 \times 10^8$ . A second infusion at the same dose will be allowed if the patient does not have improvement in respiratory parameters per discretion of the investigator, or ARDS clinically worsens, within 3-5 days following the initial infusion. When a patient is enrolled on the protocol a sufficient number of aliquoted cells will be thawed to provide the required cell dose. Thawing will be initiated on the planned date of administration according to the completed and signed Prescription for Administration received from the Principle Investigator on the study or designee. The thawed cells will be pooled, washed and formulated to the required final dose for administration. The release tests will be performed on the pooled cells prior to administration.

### 5.3.2 Administration and Monitoring of MSC Infusion

The MSCs will be given by intravenous injection, and the IV flushed with saline upon completion of the infusion. The expected volume is 20-30 mL. The rate of infusion may be tailored to patient fluid status, but the duration of infusion should not exceed 60 minutes. No other medications should be given during the infusion unless determined medically necessary by the treating physician. Patients randomized to the MSC arm must be receiving prophylactic low dose anticoagulation (or therapeutic anticoagulation if indicated for a separate etiology [i.e. atrial fibrillation, venous thromboembolism, etc.) or be considered eligible to receive at the time of study entry.

Patients may be pre-medicated with diphenhydramine up to 1mg/kg IV (max 50 mg) and/or acetaminophen up to 15mg/kg PO (max 650 mg) at least 30 minutes prior to infusion.

Monitoring will be undertaken according to institutional standards for administration of blood products, and at a minimum will be monitored according to below:

- Vitals signs (HR, BP, RR, oxygen saturation, and temperature) will be taken and recorded at the below times
  - Just prior to the start of the infusion
  - at 15, 30, 60, and 120 minutes ( $\pm$  5 minutes) after the start of the infusion
- During MSC administration, infusion *should be stopped if*:
  - the patient shows signs or symptoms of worsening respiratory status (such as tachypnea, cyanosis, complains of worsening shortness of breath, etc.) regardless of the oximetry reading.
  - there is an adverse event (AE) that the treating physician believes is related to the MSC infusion.
- No other medications should be given during the infusion unless determined medically necessary by the treating physician.
- Infusion reactions should be managed per institutional standards. Appropriate medications should be readily available at the bedside, including epinephrine, hydrocortisone, and diphenhydramine.
- If an anaphylactic reaction is suspected, the MSC administration should be stopped immediately and should not be resumed, **nor** should the patient receive any additional doses.

